6.1 Subject Disposition, Completion Rate, and Reasons for Discontinuation

Subject disposition (such as “Enrolled”, “Treated”, “Discontinued”, “Completed”, etc) will be summarized for the Enrolled Sample for the 24-month open-label treatment period. Trial completion rate and reasons for discontinuation will also be summarized.

For purposes of this trial, subjects who complete the end-of-trial visit (ie, the Month 24 visit) in the open-label treatment period will be defined as trial completers. The summary will also be repeated for subgroups defined by prior treatment status, gender, race, age group (< 15 years, \geq 15 years) and country/region. In particular, the number and percentage of subjects whose discontinuation was directly or indirectly related to the Coronavirus Disease of 2019 (COVID-19) pandemic will be presented.

Similarly, subject disposition (now restricted to “Enrolled”, “Treated” and “Enrolled into the Open-label Period”) will be summarized for the Enrolled Sample for the 1- to 4-week cross-titration conversion period.

6.2 Treatment Compliance

Treatment compliance score will be calculated and summarized only for the 24-month open-label treatment period.

Based on the IMP panel of the eSource, an individual subject’s overall compliance score with respect to taking IMP will be calculated by dividing the number of days with IMP tablets taken by the total number of days in the observed treatment period (ie, from Day 1 to the actual Last Dose date, inclusive), then multiply by 100. The numeric overall compliance score with respect to IMP will be summarized for the Safety Sample for the 24-month open-label treatment period by using descriptive statistics for continuous

variables. The overall compliance score will also be categorized (ie, into categories such as $\geq 100\%$, $\geq 80\%$ and $< 100\%$, $\geq 60\%$ and $< 80\%$, etc) and will be tabulated by category. Refer to [Section 10.6](#) for descriptive statistics.

6.3 Protocol Deviations

Protocol deviations including types of deviations or violations (eg, deviations in entry criteria, dosing, concomitant medications, procedurals, etc) will be summarized for the Enrolled Sample separately for the open-label treatment period and the preceding conversion period. The summary will be made by country, trial site, and prior treatment group (if the parent trial data are unblinded). In addition, a subject listing of protocol deviations will also be provided describing the type or the nature of the deviation or violation on each subject.

A flagging variable taking values of “yes” or “no” will be created to indicate whether the deviation or violation was related to the COVID-19 pandemic.

7 Analysis and Reporting of Demographics and Baseline Characteristics

Baseline characteristics data include those of age, body weight, height, PANSS Total Score, PANSS Positive subscale score, PANSS Negative subscale score, Clinical Global Impression – Severity of illness (CGI-S) score, Children’s Global Assessment Scale (CGAS) score, etc.

Demographics and baseline characteristics data will be summarized separately for 2 periods: (1) the 24-month open-label treatment period, on all subjects entering the open-label treatment, and (2) wherever appropriate and data are available, for the 1- to 4-week conversion period, on a set of de novo subjects that participated in a cross-titration conversion period.

7.1 Definition of the Baseline Value

7.1.1 Baseline for the 24-month Open-Label Treatment Period

Subjects entering the 24-month open-label treatment period come from three sources: (1) rollover subjects, (2) de novo subjects who skipped over a cross-titration conversion period and directly entered the open-label treatment period, and (3) de novo subjects who were required to participate in the conversion period to achieve a brexpiprazole monotherapy target starting dose of 1, 2, or 3 mg daily at any time after Week 1, and to achieve the required washout of prohibited medications. Once these goals have been achieved as deemed by the investigator, the subject will proceed to the baseline (Day 1)

visit of the open-label treatment period. It is possible that some de novo subjects cannot achieve these goals and thus will not enter the open-label treatment period.

For rollover subjects, baseline for the 24-month open-label treatment period is simply defined as the assessment value taken on the subject at the last visit (ie, the Week 6 visit) of the double-blind treatment period of the parent trial, whereas for de novo subjects (regardless of participating in the conversion period or not), baseline is defined as the last assessment value prior to the first dose of IMP upon entering the 24-month open-label treatment period. In other words, for de novo subjects, the data imputation rule last observation carried forward (LOCF) applies in determining the baseline value pertinent to the open-label treatment period. Note that there will be no imputation of baseline values for rollover subjects.

Note that there could be a small subset of subjects who completed the parent trial but could not directly rollover to the current trial due to the COVID-19 pandemic related pause of enrollment. These impacted subjects may be allowed to enroll later on as de novo subjects into the current trial (as mentioned in [Section 3](#)). If such a de novo subject enters the open-label treatment period without undergoing a conversion period, then his or her baseline values for the open-label treatment period will simply be the same as the assessments collected at the last visit (ie, the Week 6 visit) of the parent trial.

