##### **3.7.1.1.2 De Novo Subjects**

De novo subjects, whether or not they participated in Trial 331-10-234 must attend separate screening and baseline visits to allow for completion of eligibility assessments and washout of prohibited concomitant medications, if applicable.

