### **3.7.1.1.2.3 Baseline (Open-label Treatment Period)**

If the subject is found to be eligible for the trial during the screening/conversion period, the subject will attend a baseline (Day 1) visit for the open-label treatment period. For subjects that participated in the conversion period, the baseline (Day 1) visit of the open-label treatment period will coincide with the end of the conversion period which is up to 4 weeks in duration. The following procedures will be completed during the baseline (Day 1) visit of the open-label treatment period, prior to the subject starting open-label IMP:

- Inclusion/exclusion criteria will be reviewed.
- Prior medications will be reviewed.
- A qualified and certified rater will administer the PANSS.
- A qualified rater will administer the CGI-S.
- A qualified rater will administer the CGAS.
- The investigator (or qualified designee) will administer the SAS, AIMS, and BARS.
- The investigator (or qualified designee) will complete the “Since Last Visit” version of the C-SSRS form.
- The investigator (or qualified designee) will administer the UKU and NY-AACENT.
- Body weight, height, and waist circumference will be recorded.
- Vital sign measurements (including blood pressure, pulse and body temperature) will be recorded. Blood pressure and pulse are to be measured in the following order: supine, sitting, and standing after the subject has been in each position at least 3 minutes. Vital signs are to be completed before any blood is drawn.
- Blood samples will be collected for clinical laboratory tests (hematology and serum chemistry [including prolactin, HbA1c, and TSH]) after a minimum 8-hour fast. Vital sign and ECG assessments should be completed before any blood samples are collected.

- A standard 12-lead ECG will be performed predose after the subject has been supine and at rest for at least 5 minutes. The ECG is to be completed before any blood is drawn.
- Urine will be collected for urinalysis and from all potential subjects for urine screen(s) for drugs of abuse.
- A urine pregnancy test will be performed predose for all females. The result must be negative prior to dosing.
- A serum pregnancy test will be collected for all females.
- AEs and concomitant medications will be recorded.

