7.2 Demographics and Baseline Characteristics

Demographics and baseline characteristics variables including age, race, ethnicity, gender, weight, height, and body mass index (BMI) will be summarized for the Enrolled Sample by using descriptive statistics; eg, mean, median, standard deviation (SD), minimum and maximum values, percentage, etc. Of note, baseline BMI (unit: kg/m²) will be derived by dividing baseline body weight (unit: kg) by the square of baseline height (unit: meter).

The data summary for the above-mentioned variables will be provided separately for 2 periods: (1) the 24-month open-label treatment period, on all subjects entering the open-label treatment, and (2) the 1- to 4-week conversion period, on a subset of de novo subjects that participated in the cross-titration conversion period.

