8.2.5 Electrocardiogram Data

A data summary will be provided for the 24-month open-label treatment period only, since there are no ECG measurements in the conversion period.

The ECG measurements will be made at the Week 4 and Month 6, 12, 18, and 24 visits for all enrolled subjects during the 24-month open-label treatment period. The ECG measurements will also be obtained on Day 1 upon entering the open-label treatment period for de novo subjects.

Assessment values and change-from-baseline values in each of the quantitative ECG parameters will be summarized on the OC data by visit and LOCF data for the last assessment visit.

The incidence of clinically significant changes in each ECG parameter will be summarized on the OC data by visit, as well as for the overall open-label treatment period. Refer to Appendix 3 of the protocol for the criteria for identifying ECG measurements of potential clinical relevance. Data of clinically significant changes in ECG parameters will be listed by prior treatment group, subject number, sex, age, body weight, baseline value, visit, description of the findings, and dose at onset of the event.

For the analysis of QT and QTc, data from 3 consecutive complexes (representing 3 consecutive heart beats) will be measured to determine average values. The following QT corrections will be used for reporting purposes in the clinical study report:

- 1) QTcF is the length of the QT interval corrected for heart rate by the Fridericia formula: $QTcF=QT/(RR)^{0.33}$;
- 2) QTcN is the length of the QT interval corrected for heart rate by the Food and Drug Administration (FDA) Neuropharm Division formula: $QTcN=QT/(RR)^{0.37}$.

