8.4.2 Exposure Data for the 1- to 4-week Cross-titration Conversion Period

An individual subject's days of exposure to IMP for the conversion period is calculated as: date of last dose in the conversion period – date of first dose in the conversion + 1, regardless of any treatment gaps such as dose interruptions or omissions. An individual subject's average daily dose (unit: mg/day) will be calculated as: total dose (in mg) divided by days of exposure, where total dose is the summation of the actual daily doses (in mg) taken over the conversion period.

The number and percentage of subjects exposed to IMP will be tabulated by trial week. The average daily dose will be calculated for each week and will be summarized by trial week.

9 Analysis and Reporting of Efficacy Outcomes

All efficacy analyses specified in this section will be performed on the Efficacy Sample. For each efficacy variable, the analysis (eg, data summary) and reporting will be provided for the 24-month open-label treatment period only, since there is no efficacy assessment in the conversion period on the de novo subjects that underwent a cross-titration conversion.

For both rollover and de novo subjects, efficacy assessments will be collected at Week 4 and Months 2, 3, 4, 6, 8, 10, 12, 18, and 24 during the 24-month open-label treatment period. Additionally, for the de novo subjects, efficacy assessments (with the exception of the Clinical Global Impression – Improvement scale [CGI-I]) will also be collected at Day 1 of the 24-month open-label treatment period.

All efficacy assessments will be treated as secondary outcomes (endpoints) for this trial.

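### SAP 7.1.1 gives COVID-delayed re-entrants a parent-trial Week 6 baseline in place of their pre-dose Day 1 values, so change during the gap counts as open-label change

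*SAP*

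**What the plan says.** SAP 7.1.1 gives a general rule for de novo subjects, whether or not they go through conversion: "baseline is defined as the last assessment value prior to the first dose of IMP upon entering the 24-month open-label treatment period". Rollover subjects take the parent trial's Week 6 value.

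A later paragraph of the same section makes an exception for subjects who completed the parent trial but "could not directly rollover to the current trial due to the COVID-19 pandemic related pause of enrollment". If such a subject later enters as de novo and skips conversion, "his or her baseline values for the open-label treatment period will simply be the same as the assessments collected at the last visit" of the parent trial. The only trigger is the absence of a conversion period. A missing Day 1 value is not a condition.

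The protocol treats these people as ordinary de novo entrants. Section 3.7.1.1.2: "De novo subjects, whether or not they participated in Trial 331-10-234 must attend separate screening and baseline visits". Section 3.7.1.1.2.3 lists PANSS, CGI-S, CGAS, the EPS scales, C-SSRS, UKU, NY-AACENT, weight, height, waist, vital signs, laboratory tests and ECG among the procedures that "will be completed during the baseline (Day 1) visit of the open-label treatment period, prior to the subject starting open-label IMP". The SAP expects the same data. On ECG, Section 8.2.5 states: "The ECG measurements will also be obtained on Day 1 upon entering the open-label treatment period for de novo subjects". Section 9 says that for de novo subjects the efficacy assessments other than CGI-I "will also be collected at Day 1 of the 24-month open-label treatment period".

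**The concern.** A baseline should describe the subject just before the treatment period being summarised. For a rollover subject, Week 6 does this, because Protocol 3.2.1 has open-label drug start the day after the last double-blind dose. A re-entrant is in a different position. Under SAP Section 3, someone who enters as de novo because direct rollover was missed is more than 7 days past Week 6, and no upper limit is given. Whatever happened in that interval is attributed to open-label brexpiprazole.

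The outcomes at stake are the secondary change-from-baseline summaries and the subject-level flags tied to baseline:

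- 7% weight gain or loss and BMI z-score change of 0.5 (SAP 8.2.3.1)
- lipid and glucose shifts (SAP Appendix 1)
- emergent or worsening suicidality (SAP 8.2.6.3)
- the 30% PANSS reduction (SAP 9.1)

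Late re-entrants delayed for other reasons keep the general rule, so similar subjects in the same de novo column would carry different kinds of baseline.

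The SAP is also inconsistent on baseline BMI. Section 7.2 says it "will be derived by dividing baseline body weight (unit: kg) by the square of baseline height (unit: meter"), which under the exception means Week 6 values. Section 8.2.3.1 uses Day 1 weight and height for de novo subjects and mentions no exception.

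**Working it through.** The plan gives no figure to reproduce here, so the check compares the texts and then traces what the exception does to the derived outcomes.

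**Is a Day 1 value available?** Yes. Protocol 3.7.1.1.2 and 3.7.1.1.2.3 require it of former parent-trial subjects, and SAP 8.2.5 and 9 confirm it for ECG and efficacy. If Day 1 were missed, the general rule already falls back to the last pre-dose value, normally screening. Tanner staging is done at screening and not at Day 1 (Protocol Table 3.7-2), so for that item the value displaced is the screening one. CGI-I has no baseline.

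**What enters the change score?**

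(post − Week 6) = (post − Day 1) + (Day 1 − Week 6)

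The last term is the gap change. Under the general rule, with a Day 1 value present, it drops out.

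**Weight flag.** The 7% threshold is from SAP 8.2.3.1; the proportional gap change g is assumed. Gain needed after Day 1 = 1.07/(1 + g) − 1.

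| g | Gain needed after Day 1 |
|---|---|
| +3% | 1.07/1.03 − 1 = 3.9% |
| +5% | 1.07/1.05 − 1 = 1.9% |
| +7% | 1.07/1.07 − 1 = 0% |
| −3% | 1.07/0.97 − 1 = 10.3% |

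**PANSS 30% criterion.** The threshold is from SAP 9.1, with percentage change as defined in SAP 10.8. The Week 6 total W (60 to 90) and gap change d (±10 points) are assumed. Fall needed from Day 1 = 1 − 0.7W/(W + d).

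| d | W = 60 | W = 90 |
|---|---|---|
| +10 | 1 − 42/70 = 40.0% | 1 − 63/100 = 37.0% |
| −10 | 1 − 42/50 = 16.0% | 1 − 63/80 = 21.3% |

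An assumed subject with Week 6 = 80, Day 1 = 100 and last visit = 68 has changed by −12/80 = −15% from Week 6 and by −32/100 = −32% from Day 1. With the Week 6 and Day 1 values swapped, the two results swap too, so the distortion can go either way.

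**Column means.** Shift = d × k/N, for k affected subjects in a column of N with mean gap change d. All three are assumed; d = 10 points and k = 1 to 5.

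| Column | Smallest | Largest |
|---|---|---|
| De novo, N = 20 to 50 | 10 × 1/50 = 0.2 | 10 × 5/20 = 2.5 |
| All, N = 200 to 350 | 10 × 1/350 = 0.03 | 10 × 5/200 = 0.25 |

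**What is not affected.** New-onset TEAEs are counted from the first open-label dose (SAP 8.1.1), so they do not depend on this baseline.

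**The case against.** The best defence is that this is a deliberate, prespecified choice. It gives parent-trial completers the same anchor visit as every rollover subject. A Day 1 value in someone who skipped conversion may follow washout of earlier medication, and anchoring PANSS there could overstate later improvement. That argument is reasonable for symptom scales and weaker for weight and laboratory values. However, it appears nowhere in the documents supplied, and it would apply equally to the other non-conversion de novo subjects, who keep the pre-dose baseline.

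Several narrower points stand:

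- The group is expected to be small, no inferential analysis is planned, and the primary AE endpoints are essentially untouched.
- The PANSS criterion is only one route to response under SAP 9.1. A CGI-I of 1 or 2 also qualifies, and Protocol 3.7.2.4 rates CGI-I against the condition before double-blind treatment. The PANSS figures above describe the 30% criterion, not the whole responder definition.
- Day 1 values are still collected and, for efficacy and EPS scales, remain an analysis visit in SAP Table 10.2-1, so the gap change can be recovered.
- SAP 10.3 refers baseline definitions to Section 7.1, so the exception could be read as overriding 8.2.3.1 on BMI. The SAP does not say so.
- The COVID-19 Addendum cited in the protocol was not available and might explain the exception. The SAP rule, however, does not depend on missed assessments.

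**Conclusion.** The concern holds. As written, the SAP departs from its own de novo rule for one subgroup, states no reason, and sets aside pre-dose data that the protocol requires. Change over an interval of more than 7 days outside the open-label period is then reported as open-label change.

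The textual conflict is certain. The size of its effect is not, because the documents give neither the number of such subjects nor the length of the gap. On the assumed ranges, the effect on the column for all subjects is small (0.03 to 0.25 PANSS points). In the de novo column it could reach 2.5 points, but only if 5 of 20 subjects moved by an average of 10 points in the same direction. The practical exposure is in individual flags and their listings, where a single subject can be misclassified in either direction. This should be corrected, but it does not threaten the trial's main conclusions.

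**What to change.** Delete the exception in SAP 7.1.1 so that every subject who enters as de novo takes the last pre-dose value in Trial 331-10-236 (Day 1, else screening). Add one sentence allowing the parent Week 6 value only where this trial has no pre-dose value, and flag those subjects in the listings, preferably with the gap length. Align the baseline BMI wording in 7.1.1, 7.2 and 8.2.3.1 so that weight, height and BMI come from the same day.

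The cost is one sentence deleted, one added and one cross-reference. The protocol already requires the Day 1 data, so nothing new is collected. If an interim report planned in SAP 9.2 has already been produced under the current rule, the final report should note that the baseline differs for these subjects.

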7.1.2 Baseline for the 1- to 4-week Conversion Period

The baseline value for the conversion period is applicable only to a subset of de novo subjects that were required to participate in the conversion period. The baseline is defined as the last assessment prior to the first dose of IMP in the conversion period. The LOCF rule applies. Specifically, the predose assessment at Day 1 of the conversion period will be taken as baseline; if unassessed or missing, then the assessment at screening will be taken as baseline.

7.2 Demographics and Baseline Characteristics

Demographics and baseline characteristics variables including age, race, ethnicity, gender, weight, height, and body mass index (BMI) will be summarized for the Enrolled Sample by using descriptive statistics; eg, mean, median, standard deviation (SD), minimum and maximum values, percentage, etc. Of note, baseline BMI (unit: kg/m²) will be derived by dividing baseline body weight (unit: kg) by the square of baseline height (unit: meter).

The data summary for the above-mentioned variables will be provided separately for 2 periods: (1) the 24-month open-label treatment period, on all subjects entering the open-label treatment, and (2) the 1- to 4-week conversion period, on a subset of de novo subjects that participated in the cross-titration conversion period.

7.3 Medical History and Baseline Psychiatric Evaluation

Baseline values in the following parameters related to psychiatric evaluation will be summarized on the Enrolled Sample by using descriptive statistics: PANSS Total Score, PANSS Positive subscale score, PANSS Negative subscale score, CGI-S score, and CGAS score. Medical history and psychiatric history data, updated for rollover subjects and collected for de novo subjects, will also be summarized.

The data summary for the above-mentioned parameters will be provided only for the 24-month open-label treatment period, since there are no pertinent assessments in the conversion period.

8 Analysis and Reporting of Safety Outcomes

All safety analyses specified in this section will be performed on the Safety Sample.

Standard safety variables to be analyzed include AEs, clinical laboratory tests (including prolactin), vital signs, electrocardiograms (ECGs), body weight, waist circumference, and BMI. In addition, data of extrapyramidal symptom (EPS) scales including the Simpson Angus Scale (SAS), Abnormal Involuntary Movement Scale (AIMS), and Barnes Akathisia Rating Scale (BARS) will be analyzed. Data of other scales of interest such as the Columbia-Suicide Severity Rating Scale (C-SSRS), Udvalg for Kliniske Undersogelser (UKU) Side Effects Rating Scale, New York Assessment for Adverse Cognitive Effects of Neuropsychiatric Treatment (NY-AACENT), and Tanner Staging assessment will also be analyzed.

For the parameter AE, the data summary will be provided separately for 2 periods: (1) the combined period of open-label treatment plus a 21-day follow-up, on all subjects entering the open-label treatment, and (2) the conversion period, on the subset of de novo subjects that participated in a cross-titration conversion period. Of course, the summary will be based on the Safety Sample pertinent to the period.

For the parameters such as vital signs, body weight, waist circumference, BMI, and C-SSRS, the data summary will be provided separately for 2 periods: (1) the open-label treatment period, on all subjects entering the open-label treatment, and (2) the conversion period, on the subset of de novo subjects that participated in a cross-titration conversion period.

For all other parameters as mentioned above (including clinical laboratories, ECG, EPS, UKU Side Effects Rating Scale, NY-AACENT, etc), there is no assessment in the conversion period; hence, the data summary will be provided only for the open-label treatment period.

